#### **7.5.2.1 Liver Enzymes and Total Bilirubin**

Detailed testing for liver enzymes, specifically ALT, AST, and Total Bilirubin, are done at every study visit starting with Randomization and up to month 24 and unscheduled.

Confirmed abnormalities will be characterized as moderate and severe where ULN:

Moderate: AST or ALT [ $>3 \times$  ULN (in patients without liver metastases);  $>5 \times$  ULN (in patients with liver metastases)] or (Total Bilirubin  $>2 \times$  ULN).

Severe: AST or ALT  $>3 \times$  ULN and Total Bilirubin  $>2 \times$  ULN.

In addition, the subject will be considered to have severe hepatic abnormalities for any of the following:

- ALT or AST  $> 8 \times$  ULN.
- ALT or AST  $> 5 \times$  ULN for more than 2 weeks (in the absence of liver metastases).
- ALT or AST  $> 3 \times$  ULN and INR  $> 1.5$  (If INR testing is applicable/evaluated).
- ALT or AST  $> 3 \times$  ULN with the appearance of fatigue, nausea, vomiting, right upper quadrant pain or tenderness, fever, rash and/or eosinophilia ( $>5\%$ ).

#### **7.5.3 Vital Signs**

Vital signs [temperature (in Celsius), blood pressure (mmHg), pulse rate (beats/min), and respiratory rate (breaths/min)] will be summarized by treatment group at the Screening Visit and at all study visits for actual values and change from baseline. All data will be displayed in listings by treatment group and visit.

#### **7.5.4 Electrocardiograms (ECGs)**

12-Lead ECG will be performed at the Screening visit only and summarized with the baseline characteristics summary by treatment group.

#### **7.5.5 Transrectal Ultrasound-guided Prostate Biopsy and Lesion Details**

Results from the Transrectal ultrasound-guided prostate biopsy at Screening, 12 and 24 months will be summarized in tables and displayed in data listings. Descriptive statistics will

be included for continuous endpoints and frequency and percentage for categorical endpoints. Lesion details will be summarized in a table by visit and treatment group and displayed in data listings.

#### **7.5.6 Physical Examinations**

General physical examination will be performed at Screening and any abnormal finding will be reported in the medical history form should the finding occur prior to randomization, or on the AE form post-randomization. Therefore, no physical examination data will be displayed.

A breast exam will be performed at the Screening Visit and at all study visits except the Randomization Visit. Results of the exam will be summarized in a table by treatment group and included in a subject listing. Any other abnormal findings/conditions identified during the breast exam are reported in the medical history form or AE form.

Prior digital rectal examination and current rectal examination results will be summarized by treatment group at the Screening, 6 Month, 12 Month, 18 Month and 24 Month Visits, as well as at the biannual (every 6 months) visits following the 24 Month Visit. Exam results will be also be displayed in a subject listing.

#### **7.6 Analysis of PK**

Not Applicable

#### **7.7 Analysis of PD**

Not Applicable.

#### **7.8 Subgroups of Interest**

Subgroup analyses of time to progression will be performed to evaluate the treatment effect based on the following subgroups separately: age (<65, 65 to <75, and >=75), race (white, black or African American, and the combined categories of Asian, American Indian or Alaska native, Pacific islander), and BMI (<25; 25-30; and >30).

#### **7.9 Interim Analysis (and Early Discontinuation of the Clinical Study)**

Not Applicable

## **7.10 Handling of Missing Data, Outliers, Visit Windows, and Other Information**

### **7.10.1 Missing Data**

As a general principle, no imputation of missing data will be done. Exceptions are the start and stop dates and relationship of AEs and CMs and visit windows.

All analysis will be based on available data to summarize safety and efficacy results.

However, a conservative approach to partial dates and missing adverse event relationships will be as follows:

- For survival analyses, if a subject's death month and year are provided but the day is missing, the day will be set to the first day of the month, unless other qualifying study data support survival until a later date in the same month.
- For subjects in the enzalutamide arm, adverse events with partial dates with the same month and year as the first dose date of study drug will be considered as treatment-emergent adverse events.
- For subjects in the enzalutamide arm, if an adverse event's relationship is missing, it will be assumed to be related.
- For subjects in the enzalutamide arm, if the AE or CM start day is missing, then impute the 1st of the month unless month and year are the same as the month and year of first dose of study drug, then impute AE/CM start date with the first dose date. If the start month and day are both missing, then impute 01JAN unless the year is the same as first dose date, then impute AE/CM start date with the first dose date. If the entire start date is missing, then no imputation will be performed, but the AE will be considered treatment-emergent.
- For subjects on active surveillance, if the AE or CM start day is missing, then impute the 1st of the month unless month and year are the same as the month and year of randomization, then impute AE/CM start date with the randomization date. If the start month and day are both missing, then impute 01JAN unless the year is the same as randomization date, then impute AE/CM start date with the randomization date. If the entire start date is missing, then no imputation will be performed, but AE will be considered to have occurred on or after randomization date.
- For subjects in the enzalutamide arm, if the adverse event or concomitant medication end day is missing, then impute the last day of the month unless month and year are the same as month/year of last dose of study drug, then impute last dose date. If the end month and day are both missing, then impute 31DEC unless year is the same as first dose date, then impute last dose date. If the entire end date is missing, then no imputation will be performed and the event will be considered "ongoing."
- For subjects on active surveillance, if the adverse event or concomitant medication end day is missing, then impute the last day of the month unless month and year are the same as month/year of last day of 1 year of active surveillance, then impute last date on active surveillance. If the end month and day are both missing, then impute 31DEC unless year is the same as randomization date, then impute last date on active surveillance. If the entire end date is missing, then no imputation will be performed and the event will be considered "ongoing."

All AE and concomitant medication imputation of missing dates and relationship will be

considered for tabular summaries but not for data listings. Data listings will display missing values. Subjects who do not receive the study drug to which they have been randomized will be analyzed as treated.

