#### **7.2.4 Previous and Concomitant Medications**

Prior and concomitant medications will be coded according to the World Health Organization (WHO) DDE version March 2016. Prior medications are non-study medications that are recorded and stopped prior to the screening visit date. Prior medications will be exclusively reported in data listings. Concomitant medications are those that start on or after the screening visit date. Non-medication therapies will not be coded and summaries will be limited to overall use, reason for use, and radiation details.

Concomitant medications will be summarized descriptively for each treatment group and overall by therapeutic subgroup (ATC 2nd level), chemical subgroup (ATC 4th level) and preferred name by treatment group for the FAS and displayed in data listings. Subjects taking the same medication multiple times will be counted once per medication and investigational period. A medication that can be classified into several chemical and/or therapeutic subgroups is presented in all chemical and therapeutic subgroups.

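### The partial start-date rules in SAP 7.10.1 ignore a recorded end date, so they can place a start after a known stop, contradict 7.2.4 and 7.5.1, and class an enzalutamide-arm event that ended before first dose as treatment-emergent

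*SAP*

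**What the plan says.** SAP 7.10.1 sets four partial-start branches for AEs and concomitant medications (CMs).

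- **Enzalutamide, day missing:** first of the month, with an exception where the recorded period is "the same as the month and year of first dose of study drug, then impute AE/CM start date with the first dose date".
- **Enzalutamide, month and day missing:** "impute 01JAN unless the year is the same as first dose date, then impute AE/CM start date with the first dose date".
- **AS, day missing:** first of the month, with an exception where the recorded period is "the same as the month and year of randomization, then impute AE/CM start date with the randomization date".
- **AS, month and day missing:** "impute 01JAN unless the year is the same as randomization date, then impute AE/CM start date with the randomization date".

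Two further rules set treatment-emergent status directly in the enzalutamide arm. One covers AEs "with partial dates with the same month and year as the first dose date of study drug will be considered as treatment-emergent adverse events". The other covers a wholly missing start: "If the entire start date is missing, then no imputation will be performed, but the AE will be considered treatment-emergent". In the AS arm, a wholly missing AE start is taken to be on or after randomization.

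Four other provisions bear on the result:

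- 7.2.4 defines prior medications by their stop (before screening) and confines them to listings. The tabulated class is defined by the start: "Concomitant medications are those that start on or after the screening visit date".
- 7.5.1 records AEs before randomization as medical history.
- 6.4 defines TEAEs as occurring on or after first dose (randomization for AS).
- The end of 7.10.1 applies imputed dates to tables and leaves listings showing missing values.

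**The concern.** Assigning an uncertain onset to the treatment period is a reasonable conservative convention, and 7.10.1 describes its approach as conservative. That reasoning stops when the record holds an end date earlier than first dose or randomization. The onset must then also be earlier, so nothing is uncertain about which side of the reference date it falls on. The rules still move the start to the reference date.

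The same section shows that a guard was within reach: the rule for a partial death date gives way when other study data support a later date. The start-date rules have no such clause, and neither the end-date rules nor any other section of the SAP supplies one.

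At stake are the AE and concomitant-medication tables. If the relationship of such an AE is also missing, 7.10.1 assumes it related, so an event already over before the first capsule could be tabulated as drug-related.

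**Working it through.** The SAP gives no figure on this point, so there is none to reproduce. The check applies the rules literally to illustrative records.

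**Inputs.** The branches are those of 7.10.1. Screening falls on Day -28 to -7 (Table 2). AEs are collected from consent (Table 2, footnote 16), so an AE can begin and end before first dose. Assumed dates: first dose 20 June 2017, with screening on 23 May (28 days before) or 13 June (7 days before).

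| Record | Recorded start | Known end | Imputed start | Start minus end |
|---|---|---|---|---|
| (a) Medicine | 2017 only | 10 Feb 2017 | 20 Jun 2017 | +130 days |
| (b) Medicine | June 2017 | 5 Jun 2017 | 20 Jun 2017 | +15 days |
| (c) AE, enzalutamide | June 2017 | 15 Jun 2017 | 20 Jun 2017 | +5 days |
| (d) Medicine | May 2017 | 20 May 2017 | 1 May 2017 | -19 days |

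**Medicines.**
- Record (a) stopped before screening, so it is prior under 7.2.4 and belongs in listings only. Its imputed start is after screening, so it also meets the definition of concomitant. The two rules disagree.
- Record (b) meets the start-based definition of concomitant on either screening date. With screening on 13 June it is also prior by its stop, and the conflict recurs. With screening on 23 May it is not prior, and calling it concomitant is defensible.
- Record (d) shows that a partial start outside the reference month is not inverted.

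**Adverse events.** Record (c) is treatment-emergent twice over: by its imputed start under 6.4, and by the direct rule in 7.10.1. What else applies depends on randomization.
- If randomization was after 15 June, the event was over before randomization. 7.5.1 makes it medical history, so the sections contradict each other.
- If randomization was on or before 15 June and the event began after it, the medical-history rule does not reach it. It is then counted as treatment-emergent although it ended 5 days before first dose. This is a plain miscount.

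In the AS arm the reference date is randomization itself. An AE known to have ended before it is medical history under 7.5.1 but starts at randomization under 7.10.1, which is a contradiction between the sections.

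**Reach of the branches.** In a 365-day year, every end date that precedes the reference date and shares its month (5373 of 5373 combinations) or its year (66430 of 66430) gives a start after the stop. This follows directly from the rule and says nothing about frequency. Averaged over all reference dates in the year, the month branch reaches back about 15 days and the year branch 182 days. These are calendar days, not records.

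**Effect of the guard.** With the start taken as the earlier of reference date and known end, (a) starts on 10 February and is prior only. Record (c) starts on 15 June and is not treatment-emergent.

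**The case against.** The strongest reply is that 7.10.1 should be read with the rest of the SAP. 7.2.4 sends a medicine stopped before screening exclusively to listings, so record (a) should never reach the concomitant table. One may even argue that it is not a CM and that its start is not imputed at all. 7.5.1 removes pre-randomization AEs. Under 6.4, a Day 1 event whose onset box is marked as before first dose also becomes medical history. A medicine stopped between screening and first dose was in use during the study, and tabulating it is defensible.

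Much of this stands. It means that the SAP more often conflicts with itself than plainly miscounts. It does not remove the point: 7.10.1 does not defer to 7.2.4 or 7.5.1, its direct treatment-emergent rules say the opposite, a blank Day 1 box counts as treatment-emergent, and none of these provisions covers an AE that both began and ended between randomization and first dose.

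A reader might infer three stronger things that the document does not support.

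- **That the tables will necessarily include many items finished before treatment.** Reading 7.2.4 and 7.5.1 as controlling keeps most of them out.
- **That negative durations will distort reported results.** 7.2.4 and 7.5.1 plan counts of subjects and events, with no AE or medication duration.
- **That about half of the relevant records are affected.** For a 30-day month and a uniform first-dose day, the mean of (30 - k)/30 over k = 1 to 28 is 0.517. That is the share of the 28 pre-dose calendar days falling in the first-dose month. It is not a share of records or subjects, and many of those days may precede randomization.

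**Conclusion.** The point holds as a minor specification fault. Taken literally, 7.10.1 produces starts after known stops in both arms and contradicts 7.2.4 and 7.5.1. Clear miscounts of AEs are confined mainly to enzalutamide-arm events that ended between randomization and first dose. For medicines, and for AEs in the AS arm, the result is mainly a contradiction that the programmer would have to settle without guidance.

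The effect is limited to records with a partial or wholly missing start and a known end before the reference date. The SAP does not allow their number to be derived. The primary endpoint is not affected. The conclusion rests on the text of the rules; the dates in the worked records are assumed and only illustrate them.

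**What to change.** Add to 7.10.1, for both arms:

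> Imputation to first dose (randomization for AS) applies only if the end date is missing or falls on or after that date; otherwise the imputed start is the earlier of that date and the known end date. An AE with a known end before first dose (randomization for AS) is not treatment-emergent, including when its start date is wholly missing. A medicine with a known stop before screening is prior; one with a known stop on or after screening and an imputed or missing start is concomitant.

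The two direct treatment-emergent rules for the enzalutamide arm, and the AS rule for a wholly missing start, should be made subject to this text.

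Falling back to the first of the month or 1 January would be a poorer choice. A medicine with a year-only start that stopped between screening and first dose would then start before screening and stop after it, making it neither concomitant nor prior under 7.2.4. That fallback also gives no usable start when the whole date is missing.

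The cost is a short addition to the SAP and one check in the derivation program. No event of uncertain timing is lost, and no additional data are needed.

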## 4 SAMPLE SIZE

This study is designed to evaluate time to prostate cancer progression (pathological or therapeutic progression) as the primary endpoint. The overall two-sided type I error for this study is set at 0.05 level. The characteristics of time to prostate cancer progression (pathological or therapeutic progression) are used to determine the total sample size and overall duration.

A sample size of 222 subjects randomized in a 1 to 1 manner accrued over one year, a study duration of 3 years, loss-to follow-up of 16%, an assumed underlying hazard ratio of 0.52 and a three year median time-to-progression for the Control group (0.2310 rate) will result in 72 events (Fleshner et al., 2012). This sample size is sufficient to power this study at 80% with a two-sided type I error rate of 5%.

The assumed hazard ratio of 0.52 is consistent with Fleshner et al. (2012). Specifically, the Fleshner study is powered to detect a 39% failure rate reduction in the treated group with respect to a three year 45% failure rate in the control group. We used a more conservative 30% failure rate reduction for the treated group and a 50% three year failure rate for the control group. This resulted in parameter estimates of 0.2310 for the Control group and 0.1189 for the Treatment group, and thus, resulted in the hazard rate of 0.52.

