## 7 STATISTICAL METHODOLOGY

### 7.1 General Considerations

In general, descriptive statistics are defined for continuous variables as number of subjects (n), mean, standard deviation, minimum, median and maximum, and as frequency and percentage for categorical variables.

In summary and analysis tables of continuous variables, the minimum and maximum statistics will be presented to the same number of decimal places as the original data. The mean, median, quartile, and 2-sided 95% confidence interval (CI) will be presented to 1 more decimal place than the original data. The standard deviation and standard error will be presented to 2 more decimal places than the original data.

In summary tables of categorical variables, the number of non-missing observations and percentages will be presented. Unless specified otherwise, percentages by categories will be based on the number of subjects with no missing data. For categorical variables with missing values, an additional level of the variable will be added to the summary as “Missing” and the frequency will be displayed but no percentage.

Efficacy analysis will be conducted on the FAS and PPS. The primary analysis set for efficacy analyses will be the FAS. The PPS will be used to assess the robustness of the results from the statistical tests based on the FAS. Summaries based on FAS and PPS will be presented by planned treatment group, unless specifically stated otherwise. Safety analysis and other summaries based on SAF will be presented by actual treatment received.

Unless otherwise specified, all statistical testing will be conducted using two-sided tests with a significance level of 0.05.

All statistical analyses will be performed using SAS® v9.3 or higher. Specifications for table, figures, and data listing formats can be found in the TLF specifications for this study.

For the definition of subgroups of interest please refer to section 7.8.

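### The SAP's unrestricted as-treated sentence conflicts with analysis by planned group, leaving open the arm in which never-dosed enzalutamide men are counted in the primary analysis

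*SAP*

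**What the plan says.** - **Who is analyzed.** SAP Section 5.1 defines the FAS as every randomized subject and makes it the primary efficacy set. It settles membership, not the arm in which each man is counted.
- **General rule on arms.** SAP Section 7.1: "Summaries based on FAS and PPS will be presented by planned treatment group, unless specifically stated otherwise". The same paragraph assigns SAF summaries by the treatment actually received.
- **The sentence at issue.** SAP Section 7.10.1, after the date-imputation rules for adverse events and concomitant medications: "Subjects who do not receive the study drug to which they have been randomized will be analyzed as treated". No analysis set or endpoint is named.
- **Primary analysis.** SAP Section 7.4.1 specifies Kaplan-Meier estimates and a Cox model with treatment group as a fixed effect. It does not say whether treatment group is as randomized or as treated.
- **Who can be affected.** A footnote to the schedule of assessments (Table 2) says that study drug goes only to the enzalutamide arm. The sentence can therefore apply only to men randomized to enzalutamide.
- **Never-dosed men elsewhere.** Section 5.3 says that the SAF and FAS are equivalent. Section 8 says that they differ when a man randomized to enzalutamide leaves before his first dose.

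**The concern.** Two rules cover the same men. Section 7.1 keeps a never-dosed man in the enzalutamide arm for efficacy. Section 7.10.1, read literally, counts him by what he received, and in a two-arm trial of drug against surveillance that could mean AS. Section 7.1 yields to exceptions stated elsewhere and the SAP gives no order of precedence, so the text does not settle which rule governs the primary Cox model.

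The direction of the possible bias is what makes this worth fixing. The trial is open label, and primary therapy (surgery, radiation, focal or systemic therapy) counts as progression. A man who declines enzalutamide and goes to definitive therapy would take his early event out of the enzalutamide arm and into AS. A man randomized to AS who makes the same choice stays in AS. The transfer runs one way, and if such men progress faster than others it favours enzalutamide. In an open-label trial the choice between the two readings could also be made with outcomes in view.

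**Working it through.** **1. Reproduce the design figure.** Inputs from SAP Section 4: "The overall two-sided type I error for this study is set at 0.05 level"; 80% power; "A sample size of 222 subjects randomized in a 1 to 1 manner accrued over one year, a study duration of 3 years"; 16% loss to follow-up; "an assumed underlying hazard ratio of 0.52"; yearly hazards of 0.2310 (control) and 0.1189 (treatment), whose ratio is 0.515; 72 events.

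Schoenfeld's formula, 1:1 allocation: d = 4(1.960 + 0.842)² / (ln HR)².
- HR 0.515: 31.4 / 0.441 = 71.2, so 72 events. Power at 72 events is 80.4%.
- HR 0.52: 31.4 / 0.428 = 73.4, so 74 events. Power at 72 events is 79.2%.

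Expected events, with exponential hazards, uniform one-year accrual, three years in total and exponential loss of 16% over three years (loss hazard m = −ln 0.84 / 3 = 0.058 per year): the event probability p(λ) is the average over entry time a in 0 to 1 of λ/(λ+m) × [1 − exp(−(λ+m)(3 − a))]. This gives p(0.2310) = 0.410 and p(0.1189) = 0.240, so 111 × 0.410 + 111 × 0.240 = 45.5 + 26.6 = 72.1. The stated 72 events reproduce. The design arithmetic is not in dispute and serves only as a base for the next step.

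**2. Effect of the literal rule when the drug does nothing.** The SAP does not give k, the number of never-dosed enzalutamide men, or r, their hazard relative to other AS men. Assumed values: k = 3, 6 or 11 of 111, and r = 1, 2 or 4. AS is assumed to contain k comparable men already, so after the move it holds 111 − k ordinary men and 2k of this type. The HR is approximated by the ratio of events per person-year, with person-years = events / λ.

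Worked case, k = 6 and r = 2 (hazard 0.462, p = 0.644):
- Enzalutamide: 105 × 0.410 = 43.0 events in 186.3 person-years, rate 0.231.
- AS: 43.0 + 12 × 0.644 = 50.8 events in 186.3 + 16.7 = 203.0 person-years, rate 0.250.
- HR = 0.231 / 0.250 = 0.92.
- Rejection rate: total events D = 94, enzalutamide share a = 105/222 = 0.473, shift = √(D·a(1 − a)) × |ln HR| = 0.38, which gives about 7% two-sided instead of 5%.

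| Men moved | r = 1 | r = 2 | r = 4 |
|---|---|---|---|
| 3 | 1.00 (5%) | 0.96 (5%) | 0.92 (7%) |
| 6 | 1.00 (5%) | 0.92 (7%) | 0.86 (12%) |
| 11 | 1.00 (5%) | 0.87 (10%) | 0.76 (27%) |

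Entries are the as-treated HR with the two-sided rejection rate in brackets. By randomized arm, every cell is 1.00 (5%).

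**3. Extreme case.** Simulation of 1,500 trials with no drug effect, 111 men per arm, an assumed common event rate of 0.18 per year, and k men per arm with definitive therapy at 0.05 to 0.3 years, all k in the enzalutamide arm being undosed. Accrual, duration and loss are as in step 1.
- k = 2: as-treated HR 0.90, rejection 6%.
- k = 3: 0.86, 7%.
- k = 5: 0.79, 17%.
- By randomized arm: 0.99 to 1.00, with 4% rejection.

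**4. How far the extreme case depends on its premise.** With 5 men moved but only 2 treated early, the HR is 0.92; with 1 treated early, 0.94; with none, 0.99, which is no bias. Steps 2 and 3 count definitive therapy as an event, as Section 6.4 defines it.

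**The case against.** The strongest reply is that the SAP already protects the primary analysis. Section 5.1 puts all randomized men in the primary set, and Section 7.1 presents that set by planned group and the SAF by actual treatment. The disputed sentence closes a list made up almost wholly of rules on adverse-event and medication dates, so it may simply restate the SAF rule. An exception to Section 7.1 should be specific, and this sentence names no efficacy set or endpoint. Section 8 anticipates never-dosed men and changes only the relation of FAS to SAF, which fits their staying in the FAS as randomized. The SAP also never says that an undosed man counts as AS.

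Much of this stands. A reader might infer that the sentence overrides analysis by randomized arm and would certainly move men in the primary test. The documents do not support that: no precedence is stated and a safety-only intent is plausible. A reader might also take "All analysis will be based on available data to summarize safety and efficacy results", earlier in Section 7.10.1, as extending the sentence to efficacy. That line concerns the use of available data, not arm assignment.

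The reply on size is also fair. The HR of 0.79 needs every one of five undosed men to have very early definitive therapy. Men who leave the study undosed are censored close to time zero and shift almost nothing.

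What the reply does not do is close the gap. If the sentence were only about safety it would repeat Section 7.1. It is worded without limit, and Section 7.4.1 does not say which arm applies.

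**Conclusion.** The point holds as an unresolved contradiction. Sections 7.1 and 7.10.1 allow two arm assignments for never-dosed enzalutamide men, and nothing in the primary analysis section chooses between them. It does not hold as a finding that the SAP has abandoned analysis by randomized arm.

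The size of any bias cannot be fixed from the document, because the SAP gives neither the number of undosed men nor their hazard. It is nil if no such men occur or if they progress like other AS men. It is modest, a null HR of 0.92 to 0.86 and 7% to 12% rejection, with 6 of 111 moved at 2 to 4 times the AS hazard. The 0.79 is an extreme illustration, not an estimate. Where there is bias under these assumptions, it favours enzalutamide. The point deserves correction because the sentence, followed literally, would break the randomized comparison in the primary test, and the repair is small.

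**What to change.** - **Section 7.10.1:** limit the sentence to SAF summaries, or delete it, since Section 7.1 already covers the SAF.
- **Section 7.4.1:** state that all FAS and PPS efficacy analyses count each man in his randomized arm, whether or not he took study drug.
- **Sections 5.3 and 8:** reconcile them on whether never-dosed enzalutamide men are in the SAF and, if they are, under which group they are shown.

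The cost is a few clauses and no new data. Analysis by randomized arm does dilute a real effect: if undosed men have the AS hazard and the true HR is 0.52, the approximation used in the working gives power of about 74% with 6 undosed men and about 70% with 11, against about 79% with none. That is the usual price of keeping the randomized comparison, and it leaves the null rejection rate at 5%.
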